To estimate the prevalence following formula will be used to determine the sample size by doing finite population correction:

$$n = \frac{z^2 pqN}{d^2 \times (N - 1) + z^2 pq}$$

Where,

n= required sample size,

z= z-value of standard normal distribution at a given level of significance

p=prevalence of the event (Prevalence of clinically suspected dry beriberi patients show positive response to thiamine trial, usually from previous study)

q=100-p

d= allowable error/precision in the estimate of 'p'= usually 10% of p

N= Expected number of suspected dry-beriberi patients admitted in Neurology and Medicine department of CMCH during data collection period.

Here,

$z= 1.96$ at 95% confidence level

$p=80\% = 0.8$ [Prevalence of clinically suspected dry beriberi patients show positive response to thiamine trial is not available from extensive literature search. However, from our experience, 80% of these patients show positive response].

$q= (100-80)\% = 20\% = 0.2$

$d=10\% \text{ of } p = .1 \times .7 = .07$

$N= 75$

$$\text{So, } n = \frac{1.96^2 \times 0.8 \times 0.2 \times 75}{(.08)^2 \times (75-1) + 1.96^2 \times 0.8 \times 0.2} = 41.6 \approx 42$$

However, final sample size will be increased to 55 assuming 30% drop out.

5.8. Data collection tool:

- A predesigned Case Record Form.

5.9. Procedure of collecting data:

All patients attending the above mentioned ward with a diagnosis of suspected dry beriberi will be assessed for eligibility. Informed written consent will be obtained from the patients or attendants after full explanation of the ultimate outcome, complications and purpose of the study. They will be informed of their right to withdraw from the study at any stage. After consenting, the details of the patient's history including demographic information, food habit, clinical findings at presentation, results of laboratory, and neuroimaging testing will be recorded in case record form. A general physical examination (e.g. pulse, blood pressure, respiratory rate), neurological examination (higher mental function, cranial nerves, Motor, sensory, cerebellar function), results of laboratory and electro-diagnostic testing (if necessary) were recorded in case record form. Then therapeutic trial of Inj. Thiamine is given IV for 1st week (200mg IV daily) then orally (tab. Thiamin 100mg bd) for 12 weeks. Patients will be followed up after 1, 6 and 12 week to see the response.

5.10. Data analysis:

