All the data will be checked and edited after collection. Continuous data will be reported as the means \pm SD or median and itraquartile range. Qualitative or categorical data will be described as frequencies and proportions. Proportions will be compared using chi-square or Fisher's exact test whichever will be applicable. To determine whether any of the difference between pretreatment and post treatment values were statistically significant or not, either Friedman's test or Cochran's Q test were used. Former test compares the quantitative variables and non-dichotomous qualitative variables and the later test compares the dichotomous qualitative/categorical variables. Statistical significance will be defined as $P < 0.05$ and confidence interval will be set at 95% level. SPSS (Statistical Package for Social Science) for Windows version 23 software will be used for the analyses.

5.11. Variables under study:

Primary Outcome Variable:

1. Treatment response measured by Overall Neuropathy Limitation Scale (ONLS) score before and after treatment.

Secondary Outcome Variables:

1. Comparison and Assessment of clinical features at presentation and after treatment: leg swelling, muscle cramp, muscle power (MRC grading), deep tendon reflexes, sensory impairments (tingling /burning /pain/ touch/ position /vibration), squat test.

5.12 Operational definition:

Risk factors: Imbalanced diet (diet poor in thiamine/rich in anti-thiamine factors), malnutrition, alcoholism, GIT surgery, chronic diarrhea, chronic vomiting ,pregnancy, diuretics, renal dialysis, total parenteral nutrition.

Anti-Thiamine factors: Raw or fermented fish,shell fish,ferns, Tea, coffee, betel nuts

Possible/suspected dry beriberi: Risk factors + at least 2 of the following signs:

- a) Muscle weakness of upper and or lower limb (less than grade 5 power in MRC scale)
- b) Positive sensory symptoms (burning, tingling or pain)
- c) Objective sensory deficit (pain, touch, position, vibration sense)
- d) Absent or reduced deep tendon reflexes
- e) Positive squat test (unable to rise after squatting without help)
- f) Leg swelling

Probable dry beriberi: Above symptoms recovered after thiamine treatment.

Socio-economic status: It will be measured as per Modified Kuppuswamy Socio-economic scale (Appendix-A) and grouped into five categories :Upper class, Upper middle class, Lower middle class, Upper lower class and Lower class.

5.14. Utilization of results:

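### Section 5.7 sizes the study on a response proportion that 5.10 to 5.12 do not define or plan to estimate, and at the plan's own 30% drop-out the 55 enrolled fall short of its precision.

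*Combined protocol and SAP*

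**What the plan says.** Section 5.7 (Sample size) applies a precision formula for a single proportion with a finite population correction. The target is "p=prevalence of the event (Prevalence of clinically suspected dry beriberi patients show positive response to thiamine trial, usually from previous study". No published figure was found, and the value rests on clinic experience: "However, from our experience, 80% of these patients show positive response". The population size is 75, described as "N= Expected number of suspected dry-beriberi patients admitted in Neurology and Medicine department of CMCH during data collection period". The rule for d is 10% of p. The input line works this out from .7 and gets .07, while the formula uses .08. The printed result is 41.6, rounded to 42, and then: "However, final sample size will be increased to 55 assuming 30% drop out".

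The later sections concern something else. Section 5.11 gives the primary outcome as "Treatment response measured by Overall Neuropathy Limitation Scale (ONLS) score before and after treatment", with individual clinical features as secondary outcomes. For the before-and-after comparison, 5.10 says "either Friedman's test or Cochran's Q test were used". It adds a general sentence on describing categorical data and a 95% confidence level. Section 5.9 sets the visits: "Patients will be followed up after 1, 6 and 12 week to see the response". The nearest thing to a response definition is in 5.12: "Probable dry beriberi: Above symptoms recovered after thiamine treatment".

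**The concern.** The quantity that fixes the sample size does not reappear as a planned result. The ONLS outcome has no cut-off that would turn a score change into a response. The 5.12 category does not say how complete recovery must be or at which visit it is judged. The therapeutic response table in the case record form records ONLS and each feature at four assessments but has no responder field. The stated precision therefore attaches to no listed estimate.

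The second research question asks how patients respond, so a response percentage is likely to be reported. With four assessments, several features and no rule for drop-outs, its definition and denominator could be settled after the data are known. The study has no control group, and 5.14 intends the result to support a management guideline, so that percentage may carry weight.

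Separately, the precision is stated inconsistently, and the allowance for drop-out does not protect the number it is meant to protect.

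**Working it through.** **Inputs (all from 5.7).** z = 1.96; p = 0.8; q = 0.2; N = 75; d = .08 in the formula and .07 in the input line; drop-out 30%; 55 enrolled.

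**1. The plan's own figure.** n = z²pqN / [d²(N − 1) + z²pq], with z²pq = 3.8416 x 0.16 = 0.614656.
- d = .08: 46.0992 / (0.4736 + 0.614656) = 42.4. The plan prints 41.6. Both round to 42, although strict rounding up of 42.4 gives 43.
- d = .07: 46.0992 / (0.3626 + 0.614656) = 47.2.

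**2. Drop-out.** 42 x 1.3 = 54.6, which rounds to the plan's 55. A 30% loss from 55 leaves 55 x 0.7 = 38.5, so 38 or 39 evaluable. Keeping 42 after a 30% loss needs 42 / 0.7 = 60 enrolled. The loss that 55 can absorb while keeping 42 is 1 − 42/55 = 23.6%.

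**3. Expected precision.** Half-width = 1.96 x √(0.16/n), multiplied by √[(75 − n)/74] for the correction.

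| Evaluable | With correction | Without correction |
|---|---|---|
| 38 (30% loss) | 9.0 points | 12.7 points |
| 39 (30% loss) | 8.8 | 12.6 |
| 42 | 8.1 | 12.1 |
| 44 (20% loss) | 7.6 | 11.8 |
| 55 (no loss) | 5.5 | 10.6 |

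For n = 38: 1.96 x √(0.16/38) = 0.127, and 0.127 x √(37/74) = 0.090. For n = 44: 1.96 x √(0.16/44) = 0.118, and 0.118 x √(31/74) = 0.076.

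**4. Denominator.** Suppose 80% of completers respond and every drop-out counts as a non-responder. The completer and all-enrolled figures then differ by 0.8 − 0.8 x (1 − drop-out), which is 8, 16 or 24 points at 10%, 20% or 30% drop-out. As an example in patients, 30 responders are 30/38 = 79% of completers (exact 95% CI 63 to 90) and 30/55 = 55% of those enrolled (exact 95% CI 41 to 68).

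**The case against.** The strongest reply is that the plan comes close to supplying what is missing. Section 5.11 calls the ONLS outcome a treatment response, 5.12 defines a post-treatment category, and 5.10 provides for proportions and a 95% level. A reader could assemble a response proportion from these, so it would be too strong to say that the documents contain no notion of response. What stands is narrower: there is no threshold, no visit, no listed estimate and no link to p.

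A reader might also infer that 55 patients cannot deliver the precision at all. The documents do not support that. By the plan's own formula, 55 evaluable patients give 5.5 points and 44 give 7.6, both better than 8. The target is missed only when fewer than about 42 remain, and at the planned 30% the miss against .08 is about 1 point.

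The .07 is most likely a slip. The stated rule with p = 0.8 gives .08, the formula uses .08, and 42 does not depend on the odd line.

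On the correction, 5.4 limits the study population to patients admitted to these wards, and 5.14 speaks of the local setting, so using it is not plainly wrong. But the corrected figures describe only the 75 expected admissions, while a guideline would apply to later patients. Sampling is purposive (5.5), so neither half-width is a design-based guarantee.

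Finally, the 24-point gap is a worst case for an estimate proposed here. It is not an error in a planned analysis.

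**Conclusion.** The point holds in conditional form. The study is sized on a response proportion that 5.10 to 5.12 leave without a threshold, a visit, a place among the outcomes or a tie to p. Two values of d are printed (n = 42.4 at .08, 47.2 at .07), and 41.6 should read 42.4. At the plan's own 30% drop-out, about 38 rather than 42 patients are evaluable. The half-width among completers is then about 9 points with the correction, or 12.7 without, instead of 8.

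This rests on p = 0.8, N = 75, the normal approximation and a loss of the full 30%. If loss stays at or below 23.6%, the 42 are retained.

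A reader might infer that the primary analysis is undermined. It is not: the before-and-after ONLS comparison remains interpretable. The sample size was simply not derived for it, and 5.7 gives no effect size or power for that comparison. The weight of the point lies in the sample-size justification and in protecting a response percentage from being defined after the fact. It should be corrected, but it does not threaten the trial.

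**What to change.** Keep ONLS as the primary outcome and enrolment at 55.

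**Section 5.7.**
- Correct the input line to d = .1 x .8 = .08, and 41.6 to 42.4.
- State that at 30% drop-out 55 enrolled gives about 38 evaluable, with an expected half-width among completers of about 9 points with the correction and about 13 without. Note that 60 enrolled would be needed to keep 42.
- State that the 80% and the 38-completer precision refer to the completer version of the response proportion, and that applying the 80% from experience to the chosen definition is an assumption.

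**Sections 5.10 and 5.11.** Add one secondary estimate, for example: *The proportion of patients with a response at week 12 will be reported with an exact 95% confidence interval. The leading figure uses all enrolled patients and counts drop-outs as non-responders; the figure among completers is supportive.*

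**Definition, fixed before data are seen.** Use either an ONLS reduction from baseline with a cut-off confirmed by the investigators, or the 5.12 recovery definition with a visit and a degree of recovery added. If the ONLS definition is chosen, also report how many patients have a baseline ONLS of 0, since they cannot improve on it.

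**Cost.** A few sentences and one added estimate. ONLS and the clinical features are already recorded at baseline and weeks 1, 6 and 12. The downsides are a slightly less favourable stated precision and two response figures that could differ by up to 24 points in the worst case at 30% drop-out. Naming the leading figure in advance keeps that difference from becoming a choice made after the results are known.

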In our day to day clinical practice we have encountered many of them with neurological complaints mimicking thiamine deficiency (TD). Investigations to confirm this condition are not available in our setting. So, the diagnosis of TD in such contexts is a real challenge and a high level of clinical suspicion should be demonstrated in such situations. Early treatment with thiamine has the potential to rapidly reverse clinical signs and minimize sequelae, before the onset of fixed lesions. The lack of diagnostic capacity in our settings justifies the use of a therapeutic thiamine challenge in cases with high clinical suspicion. However, there is paucity of study about the clinical spectrum and therapeutic response of such patients in Bangladesh. The aim of this prospective hospital based quasi-experimental study will be to determine the clinical pattern of patients with suspected dry beriberi and their outcome to thiamine therapeutic challenge in our setting. Fifty-five patients of clinically suspected dry beriberi will be enrolled as per inclusion and exclusion criteria. Then therapeutic trial of Inj. Thiamine will be given IV for 1st week (200mg IV daily for peripheral neuropathy and then orally (tab. Thiamin 100mg bd) for 11 weeks. Patients will be followed up after 1, 6 and 12 week to see the response. Pre and post treatment data will be recorded in pre designed case record form. To determine whether any of the difference between pretreatment and post treatment values were statistically significant or not, either Friedman's test or Cochran's Q test were used. Former test compares the quantitative variables and non-dichotomous qualitative variables and the later test compares the dichotomous qualitative/categorical variables. Statistical significance were defined as $P < 0.05$ and confidence interval was set at 95% level. Analysis will be performed with SPSS version 23. Our study result is likely to sensitize the health professionals of this region about this neglected health issue by increasing awareness of the clinical spectrum of Thiamine Deficiency related Peripheral Neuropathy. Moreover, study may provide the impetus for fashioning national policies on the diagnosis, treatment and prevention of thiamine deficiency disorders in our country.

Part-D

1. Introduction:

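### Section 5.7: enrolling 55 with 30% dropout leaves about 38 completers, not the 42 required, and the margin written (0.07) is not the one used (0.08)

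*Combined protocol and SAP*

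**What the plan says.** Section 5.7 (Sample size) sizes the study as the estimation of one proportion from a finite population: "To estimate the prevalence following formula will be used to determine the sample size by doing finite population correction". The inputs are z = 1.96 "at 95% confidence level", p = 0.8, q = 0.2 and N = 75, where N is the number of suspected cases expected in the two departments during data collection. The value of p rests on clinical experience: "However, from our experience, 80% of these patients show positive response".

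The margin d is defined as "allowable error/precision in the estimate of 'p'= usually 10% of p". In the list of inputs it is worked out as 0.1 × 0.7 = 0.07. The formula line below puts in 0.08, and the result is printed as 41.6, rounded to 42.

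The dropout allowance follows: "However, final sample size will be increased to 55 assuming 30% drop out". The protocol summary gives the same enrolment target: "Fifty-five patients of clinically suspected dry beriberi will be enrolled as per inclusion and exclusion criteria".

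**The concern.** Three things in section 5.7 do not fit together.

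- **Dropout.** The allowance was added to the required number (× 1.30). It should have been taken as a loss from the enrolled number (÷ 0.70). The first method always leaves too few completers when the stated dropout occurs.
- **Margin.** Two values of d stand a few lines apart, so a reader cannot be certain which precision was planned.
- **Result.** The printed expression does not evaluate to the printed answer.

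This is the only justification given for the number of patients. Response is judged at weeks 1, 6 and 12, so a patient lost before week 12 has no final assessment, and section 5.10 gives no rule for missing visits that would recover such patients. The number of completers therefore determines the precision. Section 5.14 expects the results to feed a management guideline, so the precision claimed should be the precision the plan can deliver.

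**Working it through.** **Inputs, all from section 5.7:** z = 1.96, p = 0.8, q = 0.2, N = 75, d = 0.08 (used) or 0.07 (written), dropout 30%, final size 55.

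**Formula:** n = z²pqN / [d²(N − 1) + z²pq].

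Common terms:
- z²pq = 3.8416 × 0.16 = 0.614656
- z²pqN = 0.614656 × 75 = 46.0992

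**1. The plan's required number, d = 0.08**
- Denominator: 0.0064 × 74 + 0.614656 = 0.4736 + 0.614656 = 1.088256
- n = 46.0992 / 1.088256 = 42.36, rounded up to 43

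The plan prints 41.6 and 42. The difference is small. To obtain 41.6 one would need d of about 0.0817 or N of about 72.6, and neither appears in the plan.

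**2. The required number with the margin as written, d = 0.07**
- Denominator: 0.0049 × 74 + 0.614656 = 0.3626 + 0.614656 = 0.977256
- n = 46.0992 / 0.977256 = 47.17, rounded up to 48

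**3. Where 55 comes from**
- 42 × 1.30 = 54.6, rounded up to 55, which reproduces the plan's figure
- Completers if 30% of 55 are lost: 55 × 0.70 = 38.5, about 38
- Losses that 55 can absorb: 55 − 42 = 13, or 13/55 = 23.6%, for 42 completers; 55 − 43 = 12, or 12/55 = 21.8%, for 43

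**4. Enrolment that would keep the target after 30% loss**

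| Completers needed | Basis | Enrol (÷ 0.70, rounded up) | Share of N = 75 |
|---|---|---|---|
| 42 | as printed | 60 | 80% |
| 43 | recomputed, d = 0.08 | 62 | 83% |
| 48 | d = 0.07, only if truly intended | 69 | 92% |

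**5. Precision delivered, by the plan's own finite-population formula**

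Half-width = 1.96 × √[(pq/n) × (N − n)/(N − 1)], with p = 0.8.
- n = 38: 1.96 × √[(0.16/38) × (37/74)] = 0.0899, or 9.0 points
- n = 39: 1.96 × √[(0.16/39) × (36/74)] = 0.0876, or 8.8 points
- n = 42: 1.96 × √[(0.16/42) × (33/74)] = 0.0808, or 8.1 points
- n = 55 (no dropout): 1.96 × √[(0.16/55) × (20/74)] = 0.0550, or 5.5 points

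**The case against.** The strongest reply is that the arithmetic is wrong but little follows from it.

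- **Size of the effect.** Falling from 42 to 38 completers widens the interval from 8.1 to 9.0 points, around a p that is itself a clinical impression. This stands: the loss is modest.
- **Link to the primary outcome.** Section 5.11 makes the primary outcome the ONLS score before and after treatment, and section 5.10 compares quantitative variables by Friedman's test. The sample size concerns a responder proportion that is not listed as an outcome. This also stands: the error is not shown to weaken the primary comparison. It does not make the sample-size statement correct.
- **The 0.07 is a slip.** Very likely. The plan's rule gives 0.08, p is 0.8 throughout, and 0.08 is what was used. The figures of 48 and 69 therefore apply only if 0.07 was meant. The text still shows two margins, and the dropout error does not depend on which is right.
- **41.6 against 42.36.** On its own this moves the target by one patient.
- **The shortfall is conditional.** With all 55 assessed the half-width would be 5.5 points, and 42 completers survive dropout of up to 23.6%. That is true, but the plan itself assumes 30%.

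Reading the 30% as a simple add-on would rescue 55, but the plan calls it dropout. Nothing elsewhere in the document repairs the figures; the summary only repeats the 55.

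**Conclusion.** The point holds. On the plan's own assumptions, 55 enrolled gives about 38 completers. That is four short of the stated 42 and five short of the recomputed 43. The resulting half-width is 9.0 points, which meets neither the 8-point margin used nor the 7-point margin written. The dropout step is the substantive error. The two values of d and the misprinted 41.6 are reporting errors in the same calculation.

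The conclusion rests on p = 0.8, N = 75, a full 30% loss, and keeping the plan's finite-population correction. It should be corrected before the plan is relied on, because the stated figures are false on their own inputs. The practical cost is about one point of precision, and it does not invalidate the study.

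**What to change.** Amend section 5.7 as follows:

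1. Write d = 0.1 × 0.8 = 0.08 and remove the 0.07.
2. Replace 41.6 and 42 with 42.36, rounded up to 43.
3. Keep 55 enrolled, and state that with 30% dropout this yields about 38 completers and a 95% half-width of about 9 points by the plan's formula.

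A second option is to keep the 43-completer target and restate the tolerated dropout as about 22% (12 of 55). This is weaker, because it fits the assumption to the enrolment number and nothing in the plan supports 22%.

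If the sponsor prefers to hold the 8-point margin under 30% dropout, enrolment would be 43/0.70, that is 62. This would be 83% of the 75 cases expected, so feasibility would need checking, and the target in the summary would have to change as well.

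The first option costs a few lines of text and a slightly less favourable precision statement. It needs no extra patients.

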- What is the clinic-epidemiological profile of adult patients with suspected dry beriberi ?
- How do they response to therapeutic thiamine challenge?

3. Objectives:

3.1 General objective:

- To evaluate the efficacy of Thiamine in patients with suspected / possible dry beriberi

3.2 Specific objectives:

1. To describe the socio-demographic profile of patients
2. To categorize the patients according to their presenting symptoms and signs.
3. To assess and compare pre and post treatment neurological features

4. Rationale:

A vast population of southern area of Chittagong division of Bangladesh (Satkania, Bashkhaki, Cox'sbazar, Teknaf, Moheshkhali, Saint martin) are at risk of developing thiamine deficiency syndrome due to their dietary habit and low socio-economic condition. In our day to day clinical practice we have encountered many of them with neurological complaints mimicking thiamine deficiency (TD). However, TD has a large clinical spectrum, and as such it is frequently misdiagnosed, sometimes with fatal consequences or permanent neurological sequelae. TD can be investigated using plasma, erythrocytes, whole blood ThPP levels, and urinary excretion of thiamine before and after exogenous thiamine administration. But none of these investigations allow immediate diagnosis of TD in life-threatening conditions and they are rarely available in resource-limited settings. So, the diagnosis of TD in such contexts is a real challenge and a high level of clinical suspicion should be demonstrated in such situations. Early treatment with thiamine has the potential to rapidly reverse clinical signs and minimize sequelae, before the onset of fixed lesions. The lack of diagnostic capacity in our settings justifies the use of a therapeutic thiamine challenge in cases with high clinical suspicion. It is an effective, inexpensive, and easy to administer medication.

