19. Frank LL. Thiamine in clinical practice. *JPEN J Parenter Enteral Nutr* (2015) 39(5):503–20. doi:10.1177/0148607114565245 10

PART –E

BUDGET

I. Total Budget: 2,50,000 bdt (Two lacs and fifty thousand taka only)

II. Detailed Budget:

1. Personnel cost: Not Applicable.
2. Field Expenses/ Laboratory Costs: 1,50,000.
3. Supplies and Materials:
4. Patient Cost (if applicable): Transport fee 55,000.
5. Travel cost (Internal travel cost only) : 5000.
6. Transportation of Goods: Not Applicable.
7. Office Stationary: Internet 5000
 Stationary 5000
 Photocopy 5000.
8. Data Processing/ Computer Charges: 15,000.
9. Printing and Reproduction: 10,000.
10. Contractual Services (other than manpower): Not Applicable.
11. Administrative Overhead: Not Applicable.
12. Miscellaneous: Not Applicable.

PART-G

CASE RECORD FORM

Title: Efficacy of Thiamine in Patients with Clinically Suspected Dry Beriberi: An Open Labeled Hospital Based Study.

ID no: **Ward No:** **Bed no:** **Reg. No:**

Date of admission: **Date of Discharge:**

Date of inclusion in study:

Contact No: **Address:**

Particulars of the Patient:

1. Name:
2. Age (in years):
3. Sex: Male=1/Female=2.
4. Religion: Muslim=1/ Hindu=2/Buddist=3 / Christian=3
5. Marital Status: Married=1/ Unmarried=2/ widow=3/divorced=4.
6. Residence: urban=1/ semi urban=2/rural=3/others=4(specify).
7. Education:
8. Occupation:
9. Monthly Income:
10. Food Habit:
 - a) Rice eaten: Polished un-boiled=1/polished boiled=2
 - b) Washing before cooking:times
 - c) Discarding excess water after cooking: no=1/yes=2.
 - d) No of meals per day:

e) Contents of major meals:

Breakfast	Snacks	Lunch	Afternoon Snacks	Dinner

f) Anti-thiamine food intake: Betel nut/ tea/ fermented fish/shell fish.

.....min after major meal,.....times per day

11. Alcohol intake:

Duration.....years, Amount:...../day

current alcohol user=1/ former alcohol user=2/ never alcohol user=3.

12. Other associated conditions (if any):

GIT surgery/ Chr. Diarrhoea/ Chr. Vomitting/Renal disease/ cancer/ pregnancy/others (specify):

13. No of childbirth (in females):

Time of last childbirth:

Duration of Lactation:

12. Presenting Symptoms:

12.1) Limb Weakness: Upper limb/ lower limb/ both. Duration:.....days

12.2) Leg swelling: yes/ no. Duration.....days

Nil=0, Mild=+, moderate=++, severe=+++

12.3) Sensory Impairment (pain, tingling, numbness): yes/ no. Duration: Days.

12.4) anorexia , nausea : yes/ no. Duration: Days.

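### With 30% loss expected, no status or reason for loss recorded, and only completer tests planned, the efficacy result would describe only the patients who came back

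*Combined protocol and SAP*

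**What the plan says.** Section 5.1 describes a self-controlled pretest-posttest trial without a comparison group. Section 5.7 derives 42 patients from a precision formula and then says the "final sample size will be increased to 55 assuming 30% drop out". It does not say what counts as dropout. The 80% response it assumes has no literature source: "from our experience, 80% of these patients show positive response".

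Section 5.9 gives patients the right to withdraw and sets the visits: "Patients will be followed up after 1, 6 and 12 week to see the response". It does not ask for a reason for withdrawal or for tracing of patients who miss a visit.

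The primary outcome in section 5.11 is "Treatment response measured by Overall Neuropathy Limitation Scale (ONLS) score before and after treatment". For before/after differences, section 5.10 says that "either Friedman's test or Cochran's Q test were used". It names no analysis population, no rule for missing values and no sensitivity analysis.

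The CRF header has dates of admission, discharge and inclusion, and a contact number. Item 15 is a dated grid of scores at baseline (A0) and weeks 1, 6 and 12 (A1 to A3). Nothing in the visible form records death, withdrawal, a missed visit or the reason for one.

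**The concern.** Enrolling more patients restores the count of completers. It does not restore the outcomes of those who were lost. In item 15, a patient who died, one who worsened and went elsewhere, and one who recovered and saw no need to return would all show an empty column, with no reason beside it.

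There are grounds in the documents for expecting loss to depend on outcome. At ONLS leg grades 5 to 7 a patient needs a wheelchair to cover 10 metres or is restricted to a wheelchair or bed, and the introduction says patients come from several outlying upazilas and are mostly of low socio-economic status. In the other direction, the introduction describes rapid improvement after thiamine in severe acute deficiency, so recovered patients may also stay away.

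Without a control group, no second arm could show that loss was selective. Section 5.12 defines probable dry beriberi by recovery after treatment, so a patient who is not seen cannot be classified. Section 5.14 intends the results to support a management guideline, whose readers will want the response among all patients started on treatment.

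**Working it through.** **Inputs.** From section 5.7: z = 1.96, p = 0.80, q = 0.20, N = 75, 42 evaluable, 55 enrolled, 30% dropout. The worked formula uses d = 0.08, which is 10% of p; the line above it prints 0.07.

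**1. The plan's own figures.** n = z²pqN / [d²(N − 1) + z²pq] = (1.96² × 0.8 × 0.2 × 75) / (0.08² × 74 + 1.96² × 0.8 × 0.2) = 46.10 / 1.0883 = 42.4. The plan prints 41.6, rounded to 42, so the figure reproduces closely enough. Then 42 × 1.30 = 54.6, rounded to 55.

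**2. How many patients are lost.** There are two readings of 30%.
- 30% of those enrolled: 0.30 × 55 = 16.5 lost and 38.5 completing.
- The allowance actually built in: 55 − 42 = 13 lost, or 13/55 = 23.6%.

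(Keeping 42 completers at 30% loss would need 42/0.70 = 60 enrolled. That is a separate matter.)

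**3. What the completer result says about all enrolled.** Let r be the response among completers and m the fraction lost. Response among all enrolled lies between (1 − m)r, if every lost patient failed, and (1 − m)r + m, if every one responded. The width of the range is m itself. Assume r = 0.80; this applies the plan's planning figure to completers, which the plan does not do.
- m = 0.30: 0.70 × 0.80 = 0.56, and 0.56 + 0.30 = 0.86. In whole patients, with 31 of 39 completers responding (79.5%): 31/55 = 56.4% to 47/55 = 85.5%.
- 13 lost: 0.80 × 42 = 33.6; 33.6/55 = 61.1%, and (33.6 + 13)/55 = 84.7%.

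The ±8 points in section 5.7 are a different quantity. They express sampling error, which shrinks as more patients are enrolled. The range above comes from unseen outcomes, and enrolling more patients at the same loss rate does not narrow it.

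**4. Which patients the named tests use.** Friedman's and Cochran's Q tests both work on complete blocks: each patient needs a value at every visit compared. If all of A0 to A3 are compared, one missed visit removes the patient. If only baseline and week 12 are compared, a missing week-12 value does. On either reading, a patient who dies or does not return by week 12 is left out.

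**The case against.** A reader might infer more than the documents support, and the case against those stronger readings is good.

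- **Deaths counted inside the 30%.** Section 5.7 never defines dropout, so this would be an inference from silence. The section 5.13 flow chart was not available in the text and might show losses.
- **Only patients seen at every visit are analysed.** Section 5.10 does not say which visits enter the tests. A baseline-to-week-12 comparison needs two, and descriptive summaries at a visit need only that visit.
- **Many deaths expected.** The rationale says "sometimes with fatal consequences or permanent neurological sequelae", but of thiamine deficiency across its whole spectrum and when misdiagnosed. This trial enrols adults, excludes isolated wet beriberi and treats everyone. The documents give no mortality for treated dry beriberi.
- **The result is biased towards improvement.** Recovered patients may stay away too, and the budget line "Patient Cost (if applicable): Transport fee 55,000" may reduce travel-related loss. Not all severely disabled patients are bedbound either: a patient at leg grade 5 can still stand and walk 1 metre with help.
- **56% is what to expect.** It is an extreme. The plan has no responder definition, and its primary outcome is a score.

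It is also fair that the visit dates and the discharge date would let last contact be worked out, although not the reason for loss.

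All of this limits the claim about size and direction. It does not supply a rule for missing outcomes, a place to record why a patient was lost, or an analysis that includes that patient.

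**Conclusion.** The concern holds in a limited form. Followed as written, the plan gives an efficacy result for patients who returned, and the information needed to judge the effect of loss would be hard to recover later. This should be changed, but it does not invalidate the design.

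As an illustration of size, 80% response among completers is compatible with 56% to 86% among all enrolled at 30% loss, or about 61% to 85% with 13 lost. This rests on three assumptions: that 80% applies to completers, that response is treated as yes/no, and that lost patients all fail or all respond. Neither the actual bias nor its direction can be determined from the documents. The finding also rests on the visible CRF and text, without the flow chart. It does not depend on any particular number of deaths.

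**What to change.** 1. **CRF item 15.** For each of A1 to A3, add a status row (seen / alive, not seen / dead / unknown) with date and reason. Complete it for non-attenders through the contact number already on the form. Add consent wording that covers this contact and respects a patient's decision to withdraw.
2. **Section 5.10, proportions.** Define improvement for each sign in advance. Report the week-12 proportion improved with all enrolled patients as denominator. Count known death or withdrawal for worsening as not improved, and show unknowns under best and worst case beside the completer result.
3. **Section 5.10, tests and ONLS.** State which visits each Friedman or Cochran's Q test compares and how many patients enter it. Add an ONLS sensitivity analysis that includes patients without a week-12 value. The investigators should choose the handling of deaths in advance; several methods are defensible.

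The cost is one CRF row, a consent sentence, one extra table, and calls to roughly 13 to 17 patients, some needing more than one. Enrolment and treatment do not change. The reported response rate may look less favourable.
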